### **Outcome Measure Time Frame**

The BMI was calculated for each patient ones during one visit in the Centre. Data for all participants comes from 15 months of observation.

### **Arm/Group Information**

#### **Arm/Group Title:**

1. BMI  $\geq 35$  kg/m^2
2. BMI  $< 35$  kg/m^2

#### **Arm/Group Description:**

1. Patients with BMI  $\geq 35$  kg/m^2
2. Patients with BMI  $< 35$  kg/m^2

### **Analysis Population Information**

**Primary Outcome Measure: Outcome Measure Title:** Abnormal Plantar Pressure Distribution (APD); **Overall Number of Participants Analyzed** : 974; 1. Patients with no APD: 80; 2. Patients with APD: 894

**Secondary Outcome Measure: Outcome Measure Title:** Neuropathy; **Overall Number of**

**Participants Analyzed:** 974; 1. PSSN negative: 907 2. PSSN positive: 67

3. MN negative: calluses: 645; foot deformity: 798

4. MN positive: calluses: 329; foot deformity: 176

**Secondary Outcome Measure: Outcome Measure Title: BMI: Overall Number of**

**Participants Analyzed: 974:** 1. Patients with BMI  $\geq 35$  kg/m^2 : 153; 2. Patients with BMI <35 kg/m^2 : 821

**Outcome Measure Data Table**

**Primary Outcome Measure: Outcome Measure Title: Abnormal Plantar Pressure Distribution (APD): Outcome Measure Data Table**

**Measure Type:** count of participants

Table 1 APD in: forefoot, lateral part of the foot, mid-foot.

NT	Patients with at least one APD regardless of the location	APD within forefoot	APD within lateral part of the foot	APD within mid-foot
♂ n=451	408	380	78	5
♀ n=523	486	426	138	21
974	894	806	216	26

NT- total number of patients

APD- abnormal plantar pressure distribution

**Secondary Outcome Measure: Outcome Measure Title: Neuropathy: PSSN and MN Outcome Measure Data Table**

**Measure Type:** count of participants

Table 2. PSSN and MN (calluses and visible foot deformities) in patients with and without APD.

NT	Patients with Abnormal Plantar pressure Distribution	Patients without Abnormal Plantar pressure Distribution	NT
Patients without Peripheral Symmetric Sensory Neuropathy	833	74	907
Patients with Peripheral Symmetric Sensory Neuropathy	61	6	67
Patients without Calluses	588	57	645
Patients with Calluses	306	23	329
Patients without Foot Deformity	728	70	798
Patients with Foot Deformity	166	10	176

NT- total number of patients

APD- abnormal plantar pressure distribution

PSSN- peripheral, symmetric, sensory foot neuropathy

**Secondary Outcome Measure: Outcome Measure Title: BMI. Outcome Measure Data Table**

**Measure Type:** count of participants

Table 3. BMI <35 and BMI ≥35 in patients with and without APD within: forefoot, lateral part of the foot, mid-foot.

NT	Patients without APD within the forefoot	Patients with APD within the forefoot	Patients without APD within lateral part of the foot	Patients with APD within lateral part of the foot	Patients without APD within the mid-foot	Patients with APD within the mid-foot
BMI						
<35	128	693	665	156	808	13
821						
BMI						
≥35	40	113	93	60	140	13
153						

BMI- body mass index; NT- total number of patients

APD- abnormal plantar pressure distribution

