**Period(s):**

All medical records were analyzed between September 2012 and January 2014.

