**2. Baseline Characteristics:**

**Arm/Group Information**

Table 1. Baseline characteristics of the study population: sex, age, BMI

NT	Age (years) mean $\pm$ SD (range)	BMI (kg/m  ) mean $\pm$ SD (range)
974	64.6 $\pm$ 11.15 (21-90)	29.9 $\pm$ 5.22 (18.5-66.7)
451♂	63.8 $\pm$ 10.9 (24-90)	29.44 $\pm$ 4.74 (18.5-46.2)
523♀	65.3 $\pm$ 11.33 (21-88)	30.4 $\pm$ 5.56 (19-66.7)

NT- total number of patients    SD-standard deviation

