### **Baseline Measure Description**

**Age-** was calculated based on patients ID (identification) number (in Poland each ID number contains date of birth).

**Sex:** based on information from medical records

**BMI:** BMI was calculated based on the height and weight assessed during the visit and recorded in the medical records. BMI was defined as the body mass in kilograms divided by the square of the body height in meters, and expressed in units of  $\text{kg}/\text{m}^2$

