### Statistical Analyses

#### Statistical Analysis Overview

The Statistica 9 PL (StatSoft) software package was used for statistical analysis.

The Kolmogorowa - Smirnowa test was used in the distribution analysis.

According to the result of the analysis the parametric, T-test or nonparametric, U Mann-Whitney test was used in further calculations.

The Chi-square test was used to determine the association between two categorical variables.

A *P* value <0.05 was considered statistically significant.

Data are presented as means ( $\pm$ S.D.).

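### BMI is recorded as a number for all 974 patients, but its association with abnormal pressure distribution (APD) is shown only at one unexplained cut of 35 kg/m², which gives no slope and no shape

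*Combined protocol and SAP*

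**What the plan says.** All references are to the Combined protocol and SAP.

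- **BMI is a number.** Baseline Measure Description: "BMI was calculated based on the height and weight assessed during the visit and recorded in the medical records". The Outcome Measure Time Frame for BMI adds: "The BMI was calculated for each patient ones during one visit in the Centre". Table 1 of Baseline Characteristics gives the mean, SD and range for all patients as "29.9 $\pm$ 5.22 (18.5-66.7" kg/m²).
- **BMI is analysed as two groups.** The arm titles and descriptions for the BMI outcome define only ≥35 and <35. Analysis Population Information gives "Participants Analyzed: 974", with 153 at or above 35 and 821 below. No reason for the value 35 appears.
- **What is displayed.** Table 3 cross-tabulates these two groups against APD at three sites; its title reads "BMI <35 and BMI ≥35 in patients with and without APD within" and then lists the sites. No other BMI–APD result is shown.
- **What tests are listed.** Statistical Analysis Overview names the chi-square test for pairs of categorical variables. For continuous variables, after a distribution check, it says: "According to the result of the analysis the parametric, T-test or nonparametric, U Mann-Whitney test was used in further calculations". It does not say which variables were compared this way. It lists no regression and no trend test.
- **Timing.** Under Period(s): "All medical records were analyzed between September 2012 and January 2014".

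**The concern.** BMI is a named secondary outcome, and its association with APD changes direction by site: lower odds at the forefoot with high BMI, higher odds at the lateral foot and mid-foot. The natural next question is whether this belongs only to the 153 patients at or above 35 or also runs through the 821 below it. Table 3 treats everyone from 18.5 to just under 35 as alike, so it cannot answer. It also gives no figure, such as an OR per 5 kg/m², that a reader could apply to other BMI values or compare with another study.

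What is at stake is description and precision. Whether an association exists is not in doubt at any of the three sites.

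**Working it through.** **1. Reproduce the group sizes.** Table 3 rows, without plus with APD:
- BMI <35: 128 + 693 = 665 + 156 = 808 + 13 = 821.
- BMI ≥35: 40 + 113 = 93 + 60 = 140 + 13 = 153.
- 821 + 153 = 974. Shares: 821/974 = 84.3% and 153/974 = 15.7%.
- APD totals: 693 + 113 = 806, 156 + 60 = 216, 13 + 13 = 26. These match the primary outcome table, titled "Table 1 APD in: forefoot, lateral part of the foot, mid-foot".

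**2. What Table 3 shows.** OR = (APD ≥35 × no APD <35)/(no APD ≥35 × APD <35). The 95% CI is exp(ln OR ± 1.96 × √(sum of the reciprocals of the four counts)). Chi-square is uncorrected.

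| Site | APD, ≥35 v <35 | OR | 95% CI | Chi-square (p) |
|---|---|---|---|---|
| Forefoot | 113/153 = 73.9% v 693/821 = 84.4% | (113×128)/(40×693) = 0.52 | 0.35–0.78 | 10.06 (0.0015) |
| Lateral | 60/153 = 39.2% v 156/821 = 19.0% | (60×665)/(93×156) = 2.75 | 1.90–3.98 | 30.53 (3.3×10⁻⁸) |
| Mid-foot | 13/153 = 8.5% v 13/821 = 1.6% | (13×808)/(140×13) = 5.77 | 2.62–12.71 | 23.72 (1.1×10⁻⁶) |

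At the mid-foot the smallest expected count is 153 × 26/974 = 4.08; Fisher's exact test gives p = 3.6×10⁻⁵. The comparisons stand.

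**3. What Table 3 cannot show.** Each site yields two proportions. A step at 35, a straight line on the log-odds scale and a curve can all reproduce the same two proportions, so neither slope nor shape can be recovered from the table.

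**4. Illustrative information loss.** If the effect is linear, the share of information kept is the squared correlation between BMI and the indicator for the top 153/974.
- Normal BMI: φ(z)²/[p(1−p)] with p = 0.157 and z = 1.007, so 0.2404²/0.1324 = 0.436. In effect 974 × 0.436 ≈ 425 patients.
- Lognormal BMI (mean 29.9, SD 5.22): 0.508.
- Gamma BMI with skewness 1.25: 0.589.

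The range kept is therefore about 44–59%. Under a true step at 35 nothing is lost. The BMI shape is an assumption. A normal distribution with the stated mean and SD predicts 16.4% at or above 35 (15.7% observed), but the maximum lies (66.7 − 29.9)/5.22 = 7.0 SD above the mean. None of the three shapes fits both ends of the observed range.

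**5. What the added analysis could resolve (simulation, illustrative).** The inputs are 974 patients, the same three BMI shapes, and effects matched to Table 3. Ranges run across the shapes.

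| | Lateral | Forefoot |
|---|---|---|
| Linear effect: implied OR per 5 kg/m² | 1.60–1.76 | 0.70–0.74 |
| Linear effect: power of a trend test within BMI <35 | 92% to over 99% | 48–83% |
| Step at 35: that trend test positive | 4–5% | about 5% |
| Step at 35: power of a 3-knot spline | 28–71% | 11–31% |

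Under a linear effect, the 95% limits for the OR per 5 kg/m² would be the estimate multiplied or divided by about 1.15–1.17 (lateral), 1.16–1.18 (forefoot) and 1.33–1.51 (mid-foot).

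**6. Leverage.** With only 26 mid-foot events, one extreme BMI can matter. In an illustrative simulation, changing only the mid-foot status of the patient with BMI 66.7 moved the OR per 5 kg/m² from about 1.57 to 1.93.

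**The case against.** The strongest reply is that nothing in the document is wrong. The BMI outcome is defined as two groups, its measure type is a count, and Table 3 reports exactly that. No section claims that 35 is a threshold or sets a dose–response estimate as an aim. The association is clear at every site despite the cut. All of this stands, and it makes the point an improvement and not a correction.

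A second reply is that the absence of a displayed result does not show that BMI was never analysed as a number. The document shows no t-test or Mann-Whitney result for any variable, although the Statistical Analysis Overview says that such tests were used. A comparison of BMI by APD status may be among them. If so, it would recover the trend test, and the information loss in step 4 would not apply to it. It would still give no OR per unit and no shape.

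A reader might infer more than the documents support:
- *That the 84.3% share below 35 causes the gap.* It does not; a cut at the median would also give no slope or shape. The uneven split affects only precision.
- *That about half of the BMI information has been lost.* That holds only for Table 3 as displayed, under a linear effect and an assumed distribution.
- *That a flat trend below 35 would prove a step at 35.* It would not. Forefoot power may be as low as 48%, only an exact line and an exact step were simulated, and thresholds elsewhere or plateaus were not examined.

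**Conclusion.** The point holds as a cheap improvement in description and precision. BMI is available as a number for all 974 patients, and the only BMI–APD result shown is one unexplained cut. That cut supports three valid contrasts (OR 0.52, 2.75 and 5.77) but no effect per unit of BMI and no separation of a step from a gradient.

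The counts, ORs and tests follow directly from Table 3. The 44–59% figure and the simulation results rest on assumed BMI shapes and on an exactly linear or exactly stepped effect, so they indicate scale only. The existing records could largely settle the question at the lateral foot and partly at the forefoot; at the mid-foot they support a slope but no test of shape. All these ORs are unadjusted.

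It would be tempting to conclude that Table 3 is invalid or that its significance findings are unsafe. The documents support neither reading.

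**What to change.** Add the following, labelled post hoc and unadjusted, since the records were already analysed in 2012–2014:

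1. For each site, fit a logistic regression of APD on continuous BMI and report the OR per 5 kg/m² with its 95% CI.
2. For the forefoot (168 without APD) and lateral foot (216 with APD) only, check non-linearity with a 3-knot restricted cubic spline. For the mid-foot (26 events) use a linear term only.
3. Repeat each model without the extreme BMI values (maximum 66.7), and report both sets of estimates.
4. Optionally, report the OR per 5 kg/m² within the 821 patients below 35 for the forefoot and lateral foot, stating that a null result there does not show that the association is confined to BMI ≥35.
5. Keep Table 3 as a descriptive display and give the reason for the cut at 35. If BMI was compared as a number by APD status, show that result.

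The cost is a short rerun on data already held and a presentation less simple than a 2×2 table. The shape at the forefoot may stay uncertain, and the shape at the mid-foot cannot be tested.

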### Statistical Analyses

#### Statistical Analysis Overview

The Statistica 9 PL (StatSoft) software package was used for statistical analysis.

The Kolmogorowa - Smirnowa test was used in the distribution analysis.

According to the result of the analysis the parametric, T-test or nonparametric, U Mann-Whitney test was used in further calculations.

The Chi-square test was used to determine the association between two categorical variables.

A *P* value <0.05 was considered statistically significant.

Data are presented as means ( $\pm$ S.D.).

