## **Number of Baseline Participants**

974 participants: women: 523, men: 451;

Age categories: ≤40: 36;

41-50: 51;

51-60: 233;

61-70: 333;

71-80: 269;

81-90: 52

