#### **5.Limitations and Caveats**

1. It was not possible to carry out this analysis for the different types and duration of DM due to the lack of complete data in the analysed medical records coming from the Centre. The disease duration may be connected with higher peak pressure within the feet due to the plantar contact area narrowing (showed previously in dynamic evaluation).
2. The evaluation of the neuropathy in the Diabetic Foot Centre was based on local recommendation and not on e.g. Michigan Neuropathy Screening Instrument (MNSI). However, as a research tool in the mentioned Centre were used: foot inspection, vibration sensation, monofilament testing, and questionnaire for symptoms. This tool was similar to the MNSI.
3. The semi-quantitative analysis of the pressure map (colors), the retrospective nature of the study and the nature of the Center (although the authors involved patients from only one center of a large urban area, the available data seem to be representative of the entire diabetic population).

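### Only unadjusted two-variable tests, with no effect estimates or intervals, although age, sex and BMI are held for all 974 patients; modest confounding of the BMI associations by sex is plausible but not shown

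*Combined protocol and SAP*

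**What the plan says.** The Statistical Analysis Overview is the whole analysis section. After a Kolmogorov-Smirnov check it states: "According to the result of the analysis the parametric, T-test or nonparametric, U Mann-Whitney test was used in further calculations". For categorical pairs: "The Chi-square test was used to determine the association between two categorical variables". It sets P<0.05 and presents data as means with SD. It names no regression, stratification, odds ratio, risk difference or confidence interval.

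The outcome tables give counts. The APD table ("Table 1 APD in: forefoot, lateral part of the foot, mid-foot") is split by sex. Table 3 ("BMI <35 and BMI ≥35 in patients with and without APD within" the three sites) uses BMI only at the cut of 35 and is not split by sex or age.

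The covariates are held. The baseline section gives "974 participants: women: 523, men: 451", and its table ("Table 1. Baseline characteristics of the study population: sex, age, BMI") summarises age and BMI for the whole group and by sex. On BMI it adds: "BMI was calculated based on the height and weight assessed during the visit and recorded in the medical records".

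Limitations and Caveats explains one missing analysis: "It was not possible to carry out this analysis for the different types and duration of DM due to the lack of complete data". That reason concerns diabetes type and duration. It does not cover age or sex, and the section does not mention that the comparisons are unadjusted.

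**The concern.** This is a retrospective record review, so the groups compared were not formed by design. If sex is related both to BMI and to APD at a given site, a two-variable chi-square of BMI against APD mixes the two relations. The study's own tables show that sex is related to mean BMI and to APD at two of the three sites.

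What is at stake is the size of the BMI odds ratios at the lateral foot and mid-foot, and how secure any sex difference is once BMI is allowed for. A second cost arises in Table 2 (neuropathy by APD). A chi-square p-value without an interval invites a reader to take a non-significant result as no association, although only 80 patients are free of APD.

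**Working it through.** The documents state no test statistic, p-value or effect estimate, so there is no figure of theirs to reproduce. The check starts from the counts.

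**1. Completeness.** Sex: 523 + 451 = 974. Age bands: 36 + 51 + 233 + 333 + 269 + 52 = 974. BMI: 153 + 821 = 974. The APD totals in Table 3 (forefoot 693 + 113 = 806, lateral 156 + 60 = 216, mid-foot 13 + 13 = 26) match the APD table.

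**2. Sex against BMI and age** (baseline table, Welch t-test). BMI: (30.4 − 29.44) / √(5.56²/523 + 4.74²/451) = 0.96 / 0.330 = 2.91, p = 0.004. Age: (65.3 − 63.8) / √(11.33²/523 + 10.9²/451) = 1.5 / 0.713 = 2.10, p = 0.036.

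**3. Sex against APD** (APD table, Pearson chi-square without continuity correction).

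| APD | Women | Men | p |
|---|---|---|---|
| Lateral | 138/523 = 26.4% | 78/451 = 17.3% | 0.0007 |
| Mid-foot | 21/523 = 4.0% | 5/451 = 1.1% | 0.005 |
| Forefoot | 426/523 = 81.5% | 380/451 = 84.3% | 0.25 |
| Any site | 486/523 = 92.9% | 408/451 = 90.5% | 0.16 |

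**4. Crude odds ratios, BMI ≥35 vs <35** (Table 3). OR = ad/bc; 95% CI = exp[ln OR ± 1.96 √(1/a + 1/b + 1/c + 1/d)].
- Lateral: (60 × 665)/(93 × 156) = 2.75 (1.90 to 3.98).
- Mid-foot: (13 × 808)/(140 × 13) = 5.77 (2.62 to 12.7).
- Forefoot: (113 × 128)/(40 × 693) = 0.52 (0.35 to 0.78).

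**5. The missing input.** The number of women among the 153 with BMI ≥35 is not given and must be assumed. Expected counts with BMI ≥35, from the baseline means and SDs by sex, scaled to 153:
- normal: 106.7 women + 54.3 men = 161.0, giving 101 women;
- gamma: 103.5 + 55.6 = 159.0 (sum before rounding), giving 100;
- lognormal: 100.9 + 55.4 = 156.2 (sum before rounding), giving 99;
- gamma shifted to start at 18 kg/m²: 97.8 + 55.7 = 153.6 (sum before rounding), giving 97.

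All four shapes use the same means and SDs, so 97 to 101 is not an uncertainty range. The proportional split is 153 × 523/974 = 82.

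**6. Sex-adjusted odds ratios.** The model is logit P(APD) = α + β·(BMI ≥35) + γ·(female). Once the sex split is assumed, the published margins are its sufficient statistics, so it can be fitted without patient data.

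| Women among the 153 | Lateral | Mid-foot |
|---|---|---|
| 71 | 2.96 | 6.65 |
| 82 (proportional) | 2.79 | 5.91 |
| 97 | 2.63 | 5.22 |
| 101 | 2.60 (1.79 to 3.77) | 5.08 (2.29 to 11.3) |
| 140 | 2.42 | 4.28 |

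At 101 women the fall is 1 − 2.60/2.75 ≈ 6% (lateral) and 1 − 5.08/5.77 = 12% (mid-foot). The odds ratios drop below crude only from 86 women (lateral) or 85 (mid-foot). Forefoot is 0.53 (0.35 to 0.80) at 101. The BMI p-value stays below 0.005 at all three sites from 71 to 140 women.

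**7. Sex given BMI, mid-foot.** OR 3.14 (1.16 to 8.49) at 101 women, but 2.64 (0.96 to 7.29) at 120.

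**8. Table 2 crude odds ratios with any APD.**
- Sensory neuropathy: (61 × 74)/(6 × 833) = 0.90 (0.38 to 2.16).
- Calluses: (306 × 57)/(23 × 588) = 1.29 (0.78 to 2.13).
- Deformity: (166 × 70)/(10 × 728) = 1.60 (0.81 to 3.16).

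**The case against.** The strongest reply is that little changes. At 101 women both adjusted odds ratios lie well inside the crude intervals, and even the direction of the shift depends on a split that the documents do not give. The tables are counts, the documents assert no causal BMI effect, and chi-square is a valid test of association between two categorical variables. Crude odds ratios can be worked out from the tables by any reader. The analysis ended in January 2014, so a large modelling programme would amount to a new study.

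Much of this stands. It limits the point to a small, inexpensive addition. It does not remove it: readers cannot derive adjusted estimates from the tables, and the stated reason for a missing analysis does not reach age and sex.

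Four stronger readings are tempting, and the documents support none of them:
- **That the BMI associations are produced by sex.** At every split tried they remain clear.
- **That confounding by sex affects the primary grouping or Table 2.** Sex is not clearly related to any APD (p = 0.16), and nothing tabulated shows confounding of the neuropathy comparisons, so adjusted models there are not called for.
- **That the single cut at 35 hides a gradient or a step.** No reason for the cut is given, but the documents claim neither shape, and the t-test or Mann-Whitney U test they name could compare undivided BMI. A spline analysis would be a preference.
- **That adjustment would settle confounding by age.** No table gives APD by age, and the mid-foot model recommended here leaves age out.

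**Conclusion.** The point holds as a minor one. The described analysis is unadjusted and gives no effect sizes or intervals, although age, sex and BMI are held for every patient. Modest confounding by sex of the BMI associations with lateral and mid-foot APD is plausible but not demonstrated.

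The best guess at its size is a fall of about 6% in the lateral odds ratio and 12% in the mid-foot odds ratio. This rests on an assumed 101 women among the 153 and on a main-effects model. If women are not over-represented at BMI ≥35, there is no fall. No BMI association reverses at any split tried, sex is not clearly related to forefoot APD, and age cannot be assessed from the tables. Confidence is medium, because the key cross-table is missing.

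**What to change.** In the Statistical Analysis Overview, add the following, labelled post hoc:
1. Logistic regressions of forefoot APD and of lateral APD on BMI, age and sex. Fit BMI as ≥35 vs <35, to match Table 3, and also as continuous.
2. A Firth-penalised logistic regression of mid-foot APD on BMI and sex only, with BMI in the same two forms. With 26 events, two terms give 26/2 = 13 events per term; adding age would give 26/3 = 8.7.
3. Leave calluses and deformity out of these models, because the neuropathy outcome description places them after abnormal pressure.
4. Report adjusted odds ratios with 95% CIs beside the crude ones.
5. For Table 2, report the crude odds ratios with 95% CIs worked out above. The intervals for sensory neuropathy, calluses and deformity all include 1, but each also allows a doubling of the odds.

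In Limitations and Caveats, state that the tabulated comparisons are unadjusted, that diabetes type and duration remain unadjusted, and that the mid-foot model is not adjusted for age.

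Cost: a few models and some wording, with no new data. The downsides are that the models are post hoc, that the mid-foot model stays sparse, and that the BMI odds ratios may come out slightly smaller.
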